Characterizing cortical contributions to motor sequence learning

Cortical contributions to motor sequence learning

[name], DPT, PhD. Division of Physical Therapy, Department of Rehabilitation Medicine, Emory School of Medicine

Protocol Version 1 9/20/2019

NCT04138953

Characterizing cortical contributions to motor sequence learning

Abstract:

The long-term objective initiated with this study is to determine which brain areas functionally contribute to learning a motor skill. Our primary hypothesis is that premotor cortex (PMC) is necessary to learn a new motor skill. Healthy adults (age 18-85) will be recruited to participate in this study at the Emory University Rehabilitation Hospital. Participants may undergo a MRI scan to acquire a structural image of their brain to target noninvasive stimulation, using transcranial magnetic stimulation (TMS) to one of two brain areas: PMC or primary motor cortex (M1). A third group of individuals will undergo a placebo stimulation protocol. For all three groups, stimulation will be used to create a transient 'virtual lesion' during motor skill training.

Temporarily disrupting the normal activity of these brain regions during training will allow us to determine which regions are causally involved in learning a new motor skill. The primary outcome measure will be the change in skill after training in each group. We anticipate the group receiving sham stimulation or stimulation to M1 will have greater increases in skill learning than the group receiving stimulation to PMC.

Introduction and Background:

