Inclusion Criteria. This study utilizes non-invasive brain stimulation, which is associated with minimal risk. To further minimize any risks associated with the stimulation, every subject will be informed of the potential risks of participation in the consent form and will complete a form that screens for any potential factors that could increase risk. The PI will use this information to determine eligibility. Inclusion criteria include (1) no history of movement impairment or neurodegenerative disease (2) right handedness (3) no contraindication to transcranial magnetic stimulation (TMS)¹¹ or magnetic resonance imaging (MRI).

[figure not shown]

Figure 1. Experimental Design. Visit 1 will consist of a MRI session to acquire a structural image that will allow us to identify the target site of stimulation. Visit 2 will consist of a motor learning paradigm, during which one of three TMS conditions will be applied: premotor cortex (PMC) stimulation, primary motor cortex (M1) stimulation, or sham stimulation.

Exclusion Criteria. Any participant will be excluded if they: 1) are outside the age range of 18-85, 2) have a history of head trauma or neurodegenerative disorder, or 3) report contraindications

to TMS. Participants over age 65 will be asked to complete the Montreal Cognitive Assessment, and participants with a score of 25 or lower (out of the “normal” range) will be excluded.

Experimental Design: Participants will complete up to three study visits: a MRI session and a TMS session (**Figure 1**). During the TMS session, participants will be randomly assigned to receive one of three types of stimulation during the motor learning paradigm: TMS over premotor cortex (N=20), TMS over primary motor cortex (M1, N=20), or sham TMS over premotor cortex (N=20). Groups will be gender- and age- matched. Motor performance and cortical excitability will be assessed before and after the motor learning paradigm.

MRI Acquisition

Enrolled participants may complete a MRI scan prior to the experiment to obtain a structural brain image that will be used for guided navigation during TMS protocols. T1-weighted images will be acquired at the Center for Systems Imaging at Emory University on a Siemens Prisma 3T scanner (TR = 7.4ms, TE = 3.7ms, flip angle $\theta = 6^\circ$, 1 mm isotropic resolution, scan time=3.2min). Data will be stored on Emory University’s secure network server.

TMS Procedures

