Guided navigation will be used throughout the session in real-time to ensure consistent spatial localization of TMS application. BrainSight software (Rogue Research Inc.) will be used to localize stimulation over the motor representation associated with the target muscle, which will be the first dorsal interosseous (FDI) muscle of the hand. Electromyography (EMG) will be used to measure TMS-motor evoked potentials (MEPs) of the FDI muscle during all testing conditions. The resting motor threshold (RMT) will be defined for each hemisphere as the stimulus intensity required to elicit a MEP response greater than $50\mu\text{V}$ in over 50% of trials.¹² During the motor learning paradigm, sham or real TMS pulses will be delivered over premotor cortex or M1 at a stimulation intensity of 80% RMT time-locked to the presentation of specific visual stimuli (described in further detail below). Before and after the motor task, participants will receive blocks of TMS at 120% RMT and between 30 and 80% of maximum stimulator output to create an input/output curve to evaluate cortical excitability.

Motor Sequence Learning Paradigm

A modified version of the serial reaction time task (SRTT)¹³ will be used to assess motor sequence learning in all study participants (**Figure 2**). During this task, the left hand will be placed on a button box so that the four fingers will press specified keys. Four colored squares will appear on the screen, and participants will be instructed to press the button that corresponds to a target square located beneath the four colored squares. The button presses will occur in a repeating pattern, and response time will be measured to indicate how well the pattern is learned. There will be blocks of random sequences at the beginning and end of the test blocks that will be used

[figure not shown]

Figure 2. Example trials of SRTT. Four boxes on the top of the screen correspond to four buttons on a button box. The target box on the bottom indicates which button to press. The colors change each trial so the participant cannot learn the sequence of colors.

to assess general task performance, and there will be five blocks in between that will be used to train the sequence. A follow-up block of the task will be performed 30 minutes following training to test short-term retention of skill.

Risks and Discomforts:

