A skill score (SS) will be calculated as the difference between performance on the random blocks minus the average performance on the patterned sequence in the test block to determine how well the patterned is learned. Percent change in SS will be used to index sequence-specific motor learning while controlling for general improvements in motor performance. One-way ANOVA will be used to test for differences in sequence-specific skill acquisition and sequence-specific skill retention between the groups that received different types of TMS stimulation. R statistical packages will be used for statistical analyses. Secondary statistical analyses will use a repeated measures ANOVA to examine differences in cortical excitability before and after motor training. Significance level will be set at $\alpha \leq 0.05$.

Compensation:

Participants will get \$20 for each completed study visit, to compensate them for their time and effort. If they do not finish the study, we will compensate them for the visits they have completed. They will get \$40 total if they complete two study visits.

Data Safety and Monitoring

To ensure safety and minimize risks to study subjects, the following data safety monitoring plan (DSMP) will be implemented in accordance with the Emory University IRB DSMP guidance document:

The primary risk for subjects participating in this study is the risk of seizure associated with transcranial magnetic stimulation (TMS). Although no seizures have been reported as a direct result of the type of stimulation in this study, to minimize any risk of seizure, we will not enroll individuals with a history of seizure. A TMS screening form (adapted from ¹¹) will be administered for each subject prior to beginning the study to identify potential factors that would place the subject at increased safety risk (e.g. epilepsy or epileptogenic medications).

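### Percent change in skill score has no stated reference; the only patterned blocks described before retention are stimulated training blocks, so the primary endpoint can hide or reverse a PMC effect

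*Combined protocol and SAP*

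**What the plan says.** The Abstract states the outcome as "The primary outcome measure will be the change in skill after training in each group" and the expected result as "We anticipate the group receiving sham stimulation or stimulation to M1 will have greater increases in skill learning than the group receiving stimulation to PMC". The Statistical Plan defines SS as the "difference between performance on the random blocks minus the average performance on the patterned sequence in the test block" and then adds "Percent change in SS will be used to index sequence-specific motor learning while controlling for general improvements in motor performance". It names neither the reference nor the end block of the percentage, and does not say which random blocks enter. Acquisition and retention are each compared across the three groups by one-way ANOVA.

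The Motor Sequence Learning Paradigm section gives the block order. "There will be blocks of random sequences at the beginning and end of the test blocks that will be used" to judge general performance, and "there will be five blocks in between that will be used to train the sequence". One further block follows 30 minutes after training. No patterned block before training is listed.

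On timing, the Abstract says that "stimulation will be used to create a transient 'virtual lesion' during motor skill training", and TMS Procedures places the pulses within the motor learning paradigm. No block-by-block list of stimulation on and off is given. Experimental Design adds that "Motor performance and cortical excitability will be assessed before and after the motor learning paradigm", without saying what the earlier assessment contains.

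**The concern.** SS is random minus patterned performance, so it cannot be formed without patterned trials. On the block order described, the earliest SS comes from a training block. That block falls after randomisation and within the period of assigned stimulation, and it already contains some learning.

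The hypothesis is that PMC stimulation reduces learning. If it does so from the start, it reduces both the reference and the final score. A ratio of the two can then lose the effect, and a slower learner can score a larger percentage. The trial could report no difference, or PMC ahead of sham, when sequence learning under PMC stimulation was impaired.

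**Working it through.** **Inputs.** The documents give no SS mean, SD, effect size or power, so there is no figure of the plan's own to reproduce. Every SS value and SD below is an assumption. Group sizes are 30 (Participants and Recruitment) and 20 (Experimental Design); both are shown because the document gives both.

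**1. Cancellation.** Percent change = 100 × (SS_end − SS_ref) / SS_ref. If stimulation multiplies both scores by a factor r, then r cancels, whatever the learning curve.

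**2. Size under an assumed curve.** Take sham SS in block b as 60 × (1 − exp(−0.5b)) ms, with block 1 as reference and block 5 as end.

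| Arm | Block 1 (ms) | Block 5 (ms) | Percent change | Absolute change (ms) |
|---|---|---|---|---|
| Sham | 23.6 | 55.1 | 133% | 31.5 |
| PMC, learning halved | 11.8 | 27.5 | 133% | 15.7 |
| PMC, learning rate halved (0.25) | 13.3 | 42.8 | 223% | 29.5 |
| PMC, delayed by 0.7 block | 8.4 | 53.0 | 534% | 44.7 |

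With learning halved, the final deficit is 55.1 − 27.5, about 27.5 ms before rounding, and the percentage shows none of it. Absolute change shows 31.5 − 15.7, about 15.7 ms. The last two rows put PMC above sham.

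**3. Dependence on how far the reference is affected.** Take sham from 20 to 60 ms, which is (60 − 20)/20 = 200%, and fix the PMC end score at 36 ms, 40% below sham. A PMC reference of 20 ms gives 80% (right direction), 16 gives 125% (diluted), 12 gives 200% (cancelled) and 8 gives 350% (reversed).

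**4. Is this only the near-zero-denominator problem?** Three-group ANOVA, 30 per group, 2,000 simulated trials, correlation 0.5 between the two scores.
- SD 2 ms, so every score is well measured: percent change rejects in 7 to 8% of trials with a PMC reference of 12 ms and in 100% with an unaffected reference of 20 ms. At 8 ms it rejects in 99.8%, always with PMC above sham.
- SD 25 ms: percent change rejects in only 2 to 3% of trials even with an unaffected reference, because some denominators fall near zero. End-of-training SS rejects in 97%.

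The affected reference is therefore a separate fault, visible at low noise. At realistic noise, small denominators may mask it.

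**5. A patterned pre-test as reference.** With a true reference SS of 0, percent change rejects in about 2% of trials, and PMC exceeds sham in 50 to 51%. End-of-training SS rejects in 97 to 100%.

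**6. Power, PMC against sham.** Curve of step 2, learning halved, asymptote SD 25 ms, SS noise SD 20 ms, two-sided 0.05.

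| Endpoint | 30 per arm | 20 per arm |
|---|---|---|
| Final SS | 0.97 to 0.98 | 0.88 to 0.89 |
| Absolute change from block 1 | 0.51 to 0.52 | 0.35 to 0.37 |
| Percent change from block 1 | about 0.05 | about 0.05 |

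The drop from 0.98 to about 0.5 concerns absolute change, which is not the planned endpoint. The planned percentage does no better than alpha. At these settings it also does little better with an unaffected reference (5.8% at 30 per arm, 6.9% at 20), since block-1 SS is negative in about 14% of sham and 28% of PMC participants.

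**7. Cost of using end-of-training SS.** Suppose PMC stimulation lowers SS by a constant 15 ms while it is on and leaves learning untouched. At 30 per arm, end-of-training SS rejects in 46% of trials and absolute change in about 5%.

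**The case against.** A reader might infer that the plan fixes the first training block, under stimulation, as its reference. The documents do not say so. They name no reference, give no block-level stimulation schedule, and leave the content of the earlier motor assessment open; the design figure is not available in the text reviewed. The percentage could also be meant relative to random-block performance, which needs no patterned reference, although the wording is percent change in SS. All of this stands, and it makes the point conditional.

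A reader might also infer that a wrong-direction result is to be expected. That depends on the pattern of impairment. The 0.7-block delay involves almost full catch-up (53.0 against 55.1 ms), and if stimulation leaves the reference block unaffected the direction is preserved (80% against 200%). With the noise assumed in step 6, significant reversal occurs in about 0.2% of trials.

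Finally, end-of-training SS is not a free improvement. If the last training block is stimulated, its SS mixes disrupted performance with learning, and a change score removes a constant online effect that it would keep. This stands and has to be written into the plan.

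The open readings do not rescue the percentage. A patterned pre-test would give an SS near zero, because the sequence is new, and the ratio then fails for that reason.

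**Conclusion.** The point holds in conditional form. The reference for percent change in SS is undefined, and each reference the described schedule suggests serves the primary hypothesis badly. An early training block is exposed to the treatment it is meant to adjust for; a pre-training patterned test has an expected SS near zero. Exact cancellation under proportional impairment follows from algebra alone. The 133%, 27.5 ms, 534% and power figures rest on the assumed curve and SDs, and the documents support no particular pattern of impairment. Under those assumptions the planned percentage rejects in about 5% of trials, where SS in ms has power near 0.97 at 30 per arm. An undefined reference also lets the primary endpoint be settled after the data are seen.

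**What to change.** In the Statistical Plan:

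- Drop the percentage. Compare SS in ms between arms, without dividing by or subtracting an SS from an earlier stimulated training block. The sequence is new to every participant, so SS after training is already the change from untrained.
- Use end-of-training SS for acquisition and the 30-minute follow-up SS for retention.
- Name the random and patterned blocks in each SS, including the random block paired with the follow-up.
- State which blocks are stimulated, including the first random block, the last training block and the follow-up.
- State the limit on interpretation: if the last training block is stimulated, a claim about learning should also rest on SS from a block without stimulation, such as the 30-minute block if it is confirmed to be free of TMS.
- Show SS block by block as a description of the learning curve. If a covariate is wanted, initial random-block response time can serve, provided that block is confirmed to be unstimulated.

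The change is to wording only; the blocks are already in the schedule. There are two costs. Differences between people in early SS that are unrelated to treatment are no longer removed. End-of-training SS alone can also mistake online disruption for lost learning (46% rejection under the assumed 15 ms online-only effect).

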Movement is necessary for animals to interact with their environment. Learning to coordinate motor sequences is essential for completing tasks necessary for daily living, such as tying a shoe or speaking. Recent findings in humans suggest that sequences are represented in premotor cortex once learned¹. Studies in songbirds have also shown that the premotor cortical area HVC (abbreviation used as proper name) encodes sequence-specific information²⁻⁴. In humans, dorsal premotor cortex (PMd) is involved in the planning of execution of hand movements⁵, but it is currently unknown if this premotor cortical area is also involved in the acquisition of sequences. Noninvasive brain stimulation, such as transcranial magnetic stimulation (TMS) can be used to create a 'virtual lesion,' disrupting neural activity in a specific brain region to identify whether it is causally involved in a specific behavioral process⁶⁻⁸. In this paradigm, a magnetic field passes through the skull and induces an electric current that stimulates neural tissue. This stimulation disrupts any ongoing neural processes, creating the 'virtual lesion.' This effect is temporary and does not have persistent effects when applied in the way proposed in this study. Therefore, we will use TMS to disrupt premotor cortex activity during motor learning to determine the role of human premotor cortex in sequence learning.

Aim 1: Determine the roles of premotor cortex and primary motor cortex in motor sequence learning.

Outcome Measure: Degree of sequence learning after receiving one of three types of stimulation: premotor cortex stimulation, primary motor cortex stimulation, or sham stimulation.

Aim 2: Evaluate the effect of sequence learning on motor cortical excitability.

Outcome Measure: Change in cortical excitability after sequence learning.

Exploratory Aim 3: Examine the relationship between sequence learning and cortical excitability.

Outcome Measure: Correlation between the amount of sequence learning and change in cortical excitability after learning.

Participants and Recruitment:

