Based on effects reported in previous literature using a similar experimental paradigm and participant populations^{9, 10}, we anticipate that 30 participants per group (N=90 total) will provide sufficient power to test the primary study hypotheses. Therefore, this study will recruit 90 healthy men and women aged 18-85. Subjects will be identified and recruited through multiple approaches. Local University and community postings will be used to identify and recruit the healthy control participants. Additionally, partnerships with collaborators within the Division of Physical Therapy, Emory School of Medicine and Emory Healthcare will be utilized in subject identification and recruitment. Initial contact may be made by [name] or one of his associates.

Informed Consent. The letter of informed consent will be used as a template to describe what is being asked of the participant, the risks and benefits associated with participation etc. to the participant. The consent form will be explained by a member of the research team. At this time the individual making contact will also be available to answer any specific questions that may arise. Informed consent will be conducted by either [name] or a research coordinator in private-either in the research lab or a single-occupant office.

In testing sessions performed at the Neural Plasticity Research Laboratory (NPRL), participants will undergo: 1) noninvasive targeting of cortical locations by stereotactic neuronavigation using transcranial magnetic stimulation (TMS), 2) TMS measures of cortical excitability and neurotransmitter signaling, and 3) a motor learning paradigm. The duration of the testing session will be less than 3 hours. Participants may also be asked to complete a single magnetic resonance imaging (MRI) session prior to testing in the NPRL. Overall, participants will complete up to two study visits.

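### The hypothesis is that PMC disruption impairs learning, but the only planned test of skill is a three-group ANOVA with no PMC comparison: prespecify PMC vs sham, then PMC vs M1

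*Combined protocol and SAP*

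**What the plan says.** The Abstract sets the question: "Our primary hypothesis is that premotor cortex (PMC) is necessary to learn a new motor skill". It also predicts a pattern, that the groups receiving "sham stimulation or stimulation to M1 will have greater increases in skill learning than the group receiving stimulation to PMC". On the endpoint it says: "The primary outcome measure will be the change in skill after training in each group". Aim 1 is wider: "Determine the roles of premotor cortex and primary motor cortex in motor sequence learning".

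The Statistical Plan gives one group comparison of skill: "One-way ANOVA will be used to test for differences in sequence-specific skill acquisition and sequence-specific skill retention between the groups". The variable is percent change in the skill score and the significance level is 0.05. Retention comes from a separate measurement, described under Motor Sequence Learning Paradigm: "A follow-up block of the task will be performed 30 minutes following training to test short-term retention of skill".

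No section names a pairwise comparison, contrast, post hoc test, direction, order of the two skill endpoints or multiplicity rule. The repeated measures ANOVA concerns cortical excitability, and exploratory Aim 3 is a correlation. Neither compares PMC with another group on skill.

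**The concern.** The hypothesis concerns one group and one direction. The F test asks only whether the three means are equal. With equal group sizes it responds identically to a shift in any one group, up or down. A significant result could therefore come from M1 alone, or from PMC stimulation that helps learning, and the second would contradict the hypothesis. The comparison that decides the question would then be chosen after the data are seen.

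The Statistical Plan also lists acquisition and retention side by side without saying which is primary. If either could carry the learning claim, two tests at 0.05 give a false-positive rate above 5%.

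**Working it through.** **Inputs from the documents.** There are three groups and alpha is 0.05. The size is 30 per group under Participants and Recruitment ("we anticipate that 30 participants per group (N=90 total) will provide sufficient power to test the primary study hypotheses") but 20 per group under Experimental Design, so both are used. The plan's 90 cannot be reproduced, because no effect size, SD or numerical power is given.

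**Assumptions.** Normal data, equal SDs, two-sided tests, and an effect d in SD units of 0.5, 0.71 or 0.9. The middle value is about what gives the F test 80% power at 30 per group (0.706 exactly); it is not an estimate from data.

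**F test.** If one group differs by d and the other two are equal, the deviations from the grand mean are 2d/3, −d/3 and −d/3. Their squares sum to 2d²/3, so the noncentrality is λ = 2nd²/3, on 2 and 3n−3 degrees of freedom. The group label and the sign of d drop out.
- n = 30, d = 0.71: λ = 2 × 30 × 0.5041 / 3 = 10.08; power 80%.
- n = 20, d = 0.71: λ = 2 × 20 × 0.5041 / 3 = 6.72; power 61%.

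**PMC vs sham, pooled ANOVA error.** The noncentrality is d√(n/2), on 3n−3 degrees of freedom.
- n = 30: 0.71 × √15 = 2.75; power 78%.
- n = 20: 0.71 × √10 = 2.25; power 60%.

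**What each test responds to, d = 0.71.**

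| Truth | F significant, n=30 | PMC found below sham, n=30 | F significant, n=20 | PMC found below sham, n=20 |
|---|---|---|---|---|
| Only PMC impaired | 80% | 78% | 61% | 60% |
| Only M1 impaired | 80% | 2.5% | 61% | 2.5% |
| Only PMC changed, for the better | 80% | about 0% | 61% | about 0% |

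**Other effect sizes, only PMC impaired (d = 0.5, 0.71, 0.9).**
- 30 per group: F 49%, 80%, 95%; PMC vs sham 48%, 78%, 93%.
- 20 per group: F 34%, 61%, 83%; PMC vs sham 34%, 60%, 80%.

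**Non-normal data (d = 0.71, n = 30; t with 3 df, exponential, log-normal).** F is significant in 80% to 84% whether only PMC or only M1 is impaired. PMC vs sham finds PMC lower in 78% to 81% in the first case and 2.2% to 2.4% in the second.

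**Requiring a significant F before PMC vs sham (d = 0.71, n = 30).** The plan does not state this gate. Power for PMC below sham would fall as follows:
- M1 equal to sham: 77.6% to 72.6%, a loss of 5 points.
- M1 equal to PMC: 77.7% to 72.7%, a loss of 5 points.
- M1 halfway between: 77.6% to 66.3%, a loss of 11 points.
- M1 outside that range (two patterns tried): a loss under 0.5 point.

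**PMC below both other groups (d = 0.71).** With M1 equal to sham, the probability is 66% at 30 per group (65% with an F gate) and 44% at 20 per group (43% with a gate). With M1 halfway it is 26% and 17%.

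**Two endpoints.** If a significant F on either acquisition or retention were enough, simulated familywise error is 10%, 9%, 8% and 7% at correlations of 0, 0.5, 0.7 and 0.9. Both scores come from one session, so a correlation near 0 is unlikely.

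**The case against.** The strongest reply is that nobody would read a significant F without looking at the means. When only M1 is impaired (0.71 SD, 30 per group), F is significant with PMC lowest in just 0.06% of trials. This is true for that case. It fails when PMC and M1 are equally impaired: F is then significant with PMC lowest in 40% of trials, although the predicted PMC–M1 difference does not exist. Even when only PMC is impaired, about 8% of trials have a significant F without PMC significantly below sham, and the plan does not say what would be concluded.

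A second reply is that pairwise tests after a significant F are implied, and with three groups that procedure controls the error rate. An F test followed by a named PMC vs sham test would indeed be about as specific. But the plan names no such test, so naming it is the essential repair.

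Third, Aim 1 asks about both regions, and a three-group ANOVA is a reasonable first look at that. This stands, and is why F and M1 vs sham should be kept. F alone, however, does not say which region matters.

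Fourth, comparing PMC with the average of sham and M1 has more power when M1 equals sham: at 0.71 SD, 88% against 80% for F at 30 per group, and 72% against 61% at 20. So the absence of a power gain belongs to the pairwise choice, not to every planned contrast. The averaged contrast cannot show PMC below each group, which is what the Abstract predicts.

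Fifth, PMC vs sham does not isolate PMC: it succeeds equally often (78%) if M1 is impaired to the same degree. That is correct, and is why the second step is needed.

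Finally, the Abstract's primary outcome already points to acquisition. It does, so the familywise figures apply only if the Statistical Plan is read as letting either endpoint decide.

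**Conclusion.** The concern holds. The stated test does not by itself answer the stated primary hypothesis. Its symmetry follows from the formula for equal groups and does not depend on the assumed effect size; the percentages do. They rest on assumed effects, equal SDs and mostly normal data. The analysed variable is a percent change, and the shapes tried do not model a ratio with a small baseline.

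The benefit is that a significant primary result would mean what the hypothesis says. It is not a gain in power over F alone. The false-positive concern over two endpoints is secondary and conditional. The change should be made, and the conflict between 30 and 20 per group must be reconciled before power for the comparisons can be stated.

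**What to change.** In the Statistical Plan, name skill acquisition as the single primary endpoint, in line with the Abstract. From the same one-way ANOVA model with pooled error, prespecify two tests in fixed sequence, each at two-sided 0.05:

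1. PMC vs sham.
2. PMC vs M1, tested only if step 1 is significant with PMC lower.

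Step 1 decides whether disrupting PMC impairs learning. Both steps together decide the Abstract's full prediction. Testing step 2 only after success at step 1 keeps the familywise error of the sequence at 5%. Report the omnibus F and M1 vs sham as prespecified secondary results, with estimates and 95% confidence intervals for the comparison, so that Aim 1's question about M1 is still answered. Make retention secondary.

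The cost is wording only: data collection and sample size do not change. Two downsides should be accepted openly. M1 vs sham becomes secondary, although its power is unchanged (78% at 30 per group and 60% at 20, if M1 is impaired by 0.71 SD). And the full prediction remains harder to show than step 1 alone, with almost no gain over an F gate.
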